Grade 4 (>20.0 x ULN)	

Recommended dose modifications of INC280	
Worst toxicity CTCAE v4.03 grade	Recommended dose modifications any time during a cycle of therapy, including intended day of dosing
Combined ^b elevations of AST or ALT, and Total Bilirubin	
For patients with normal baseline ALT and AST and total bilirubin value: AST or ALT >3.0xULN combined with total bilirubin >2.0 x ULN without evidence of cholestasis ^c OR For patients with elevated baseline AST or ALT or total bilirubin value: [AST or ALT>2x baseline AND > 3.0 xULN] OR [AST or ALT > 8.0 xULN] combined with [total bilirubin >2x baseline AND >2.0 xULN]	Discontinue study treatment permanently. Repeat LFTs as soon as possible, preferably within 48 hours from awareness of the abnormal results, then with weekly monitoring of LFTs*, or more frequently if clinically indicated, until AST, ALT, or bilirubin have resolved to baseline or stabilization over 4 weeks. Refer to Section 6.2.6 for additional follow-up evaluations as applicable.
Reactivation of HBV or HCV	Please refer to Table 6-7 , Table 6-8 .
*LFTs include albumin, ALT, AST, GGT, total bilirubin (fractionated [direct and indirect] if total bilirubin > 2.0 x ULN) and ALP (fractionated [quantification of isoforms], if alkaline phosphatase > 2.0 x ULN). Refer to Section 6.2.6 for additional follow-up evaluations.	
Pancreatic^d	
Asymptomatic grade 1 or 2 amylase or lipase increased (>ULN – 2.0 x ULN)	Maintain dose level
Asymptomatic grade 3 or greater amylase or lipase increased (> 2.0 - > 5.0 x ULN)	Omit/delay dose until resolved to ≤ G2, then: If resolved in ≤ 7 days, maintain dose level If resolved in > 7 days, then ↓ 1 dose level
Asymptomatic grade 4 (> 5.0 x ULN)	Discontinue does and patient form study treatment
Symptomatic elevations of any grade	Discontinue does and patient form study treatment

Recommended dose modifications of INC280	
Worst toxicity CTCAE v4.03 grade	Recommended dose modifications any time during a cycle of therapy, including intended day of dosing
Neurologic	
Any Neurological Toxicity Grade 2	Discontinue study treatment. Neurological assessments must be repeated at least twice a week until resolution to < CTCAE grade 1. Unscheduled MRI and gadolinium enhanced T1 imaging may also be conducted to evaluate patients for intramyelinic edema like lesions, brain metastases and other unanticipated CNS occurrences. An EEG may be performed to monitor for physiological changes in brain activity.
Cardiac	

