
^a If total bilirubin $> 3.0 \times$ ULN is due to the indirect (non-conjugated) component only, and hemolysis as the etiology has been ruled out as per institutional guidelines (e.g. review of peripheral blood smear and haptoglobin determination), then \downarrow 1 dose level of INC280, and continue treatment at the discretion of the Investigator
 
^b "Combined" defined as: total bilirubin increase to the defined threshold concurrently with ALT/AST increase to the defined threshold
 
If combined elevations of AST or ALT and total bilirubin do not meet the defined thresholds, please follow the instructions for isolated elevation of total bilirubin and isolated elevation of AST/ALT, and take a conservative action based on the degree of the elevations (e.g. discontinue treatment at the situation when omit dose is needed for one parameter and discontinue treatment is required for another parameter). After all elevations resolve to the defined thresholds that allow treatment re-initiation, re-start the treatment either at the same dose or at one dose lower if meeting a criterion for dose reduction
 
^c "Cholestasis" defined as: ALP elevation ($>2 \times$ULN and R value <2) in patients without bone metastasis, or elevation of ALP liver fraction in patients with bone metastasis
 
Note : The R value is calculated by dividing the ALT by the ALP, using multiples of the ULN for both values. It denotes whether the relative pattern of ALT and/or ALP elevation is due to cholestatic (R\leq2), hepatocellular (R\geq5), or mixed (R>2 and <5) liver injury
 
^d A CT scan or other imaging study to assess the pancreas, liver, and gallbladder must be performed within 1 week of the first occurrence of any \geq Grade 3 of amylase or lipase.
	

Table 6-6 Follow-up evaluations for selected toxicities

Toxicity	Follow-up evaluation
Hematology	If febrile neutropenia of any duration occurs, the patient must be followed until resolution. If \geq CTCAE grade 3 hematologic toxicity occurs, the parameter must be repeated at least twice a week until resolution to \leq CTCAE grade 1 and then at least weekly until either initiation of retreatment or until stabilization.

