For patients with baseline value $> 3.0 - 5.0 \times$ ULN:	Repeat LFTs as soon as possible, preferably within 48-72 hours from awareness of the abnormal results; if abnormal lab values are confirmed upon the repeat test, then monitor LFTs, weekly, or more frequently if clinically indicated, until resolved to $\leq 5.0 \times$ ULN
CTCAE Grade 3 For AST/ALT elevation $> 10.0 - 20.0 \times$ ULN:	Repeat LFTs as soon as possible, preferably within 48-72 hours from awareness of the abnormal results; monitor LFTs weekly, or more frequently if clinically indicated, until resolved to \leq baseline
CTCAE Grade 4	Repeat LFTs as soon as possible, preferably within 48-72 hours from awareness of the abnormal results; monitor LFTs weekly, or more frequently if clinically indicated, until resolved to baseline or stabilization over 4 weeks.
Combined elevations in ALT and/or AST with concurrent total bilirubin increase, in the absence of cholestasis or hemolysis	

Toxicity	Follow-up evaluation
Combined elevations of AST or ALT and total bilirubin	
After discontinuing the patient from INC280 permanently, repeat core LFTs as soon as possible, preferably within 48 hr from awareness of the abnormal results, then with weekly monitoring of LFTs, or more frequently if clinically indicated, until AST, ALT, or bilirubin have resolved to baseline or stabilization over 4 weeks.
 
Core LFTs consist of ALT, AST, GGT, total bilirubin (fractionated [direct and indirect], if total bilirubin $> 2.0 \times$ ULN), and alkaline phosphatase (fractionated [quantification of isoforms], if alkaline phosphatase $> 2.0 \times$ ULN.)

*Note: this table refers only to the evaluation schedule to monitor hepatic toxicities. Refer to [Table 6-5](#) for dose modifications required for applicable toxicities.

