6.2.6.1 Follow up on potential drug-induced liver injury (DILI) cases

Patients with transaminase increase combined with TBIL increase may be indicative of potential DILI, and should be considered as clinically important events.

The threshold for potential DILI may depend on the patient's baseline AST/ALT and TBIL value; patients meeting any of the following criteria will require further follow-up as outlined below:

- For patients with normal ALT and AST and TBIL value at baseline: AST or ALT $> 3.0 \times$ ULN combined with TBIL $> 2.0 \times$ ULN
- For patients with elevated AST or ALT or TBIL value at baseline: [AST or ALT $> 2 \times$ baseline AND $> 3.0 \times$ ULN] OR [AST or ALT $> 8.0 \times$ ULN], combined with [TBIL $> 2 \times$ baseline AND $> 2.0 \times$ ULN]

Medical review needs to ensure that liver test elevations are not caused by cholestasis, defined as: ALP elevation $> 2.0 \times$ ULN with R value < 2 in patients without bone metastasis, or elevation of ALP liver fraction in patients with bone metastasis.

Note: (The R value is calculated by dividing the ALT by the ALP, using multiples of the ULN for both values. It denotes whether the relative pattern of ALT and/or ALP elevation is due to cholestatic (R ≤ 2), hepatocellular (R ≥ 5), or mixed (R > 2 and < 5) liver injury)

In the absence of cholestasis, these patients should be immediately discontinued from study drug treatment, and repeat LFT testing as soon as possible, preferably within 48 hours from the awareness of the abnormal results. The evaluation should include laboratory tests, detailed history, physical assessment and the possibility of liver metastasis or new liver lesions, obstructions/compressions, etc.

- Laboratory tests should include ALT, AST, albumin, creatine kinase, total bilirubin, direct and indirect bilirubin, GGT, prothrombin time (PT)/INR and alkaline phosphatase.
- A detailed history, including relevant information, such as review of ethanol, concomitant medications, herbal remedies, supplement consumption, history of any pre-existing liver conditions or risk factors, should be collected.
- Further testing for acute hepatitis A, B, C or E infection and liver imaging (e.g., biliary tract) may be warranted.
- Obtain PK sample, as close as possible to last dose of study drug, if PK analysis is performed in the study.

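### For patients with abnormal baseline liver tests, Table 6-5 requires a permanent stop at the combined ALT/AST and bilirubin threshold whether or not cholestasis is present, while Section 6.2.6.1 makes the stop conditional on its absence

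*Protocol*

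**What the plan says.** **Protocol Section 6.2.5, Table 6-5, combined elevations.** Two alternative criteria are joined by OR and share one action, "Discontinue study treatment permanently".

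- Normal baseline: "AST or ALT >3.0xULN combined with total bilirubin >2.0 x ULN without evidence of cholestasis". The cholestasis condition is part of this criterion and carries the marker for footnote c.
- Elevated baseline: "For patients with elevated baseline AST or ALT or total bilirubin value: [AST or ALT>2x baseline AND > 3.0 xULN", or alternatively "AST or ALT > 8.0 xULN] combined with [total bilirubin >2x baseline AND >2.0 xULN". Nothing on cholestasis or haemolysis follows.

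Footnote b sends patients to the isolated-bilirubin and isolated-transaminase rows only if their combined elevations fall short of the thresholds. Footnote c defines cholestasis as ALP above 2 x ULN "and R value <2) in patients without bone metastasis", or a raised ALP liver fraction if there is bone metastasis.

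**Protocol Section 6.2.6.1.** It lists the same numerical thresholds for both baseline groups, asks for medical review to exclude cholestasis, and then says: "In the absence of cholestasis, these patients should be immediately discontinued from study drug treatment".

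**Protocol Section 6.2.6, Table 6-9.** The combined block is headed "Combined elevations in ALT and/or AST with concurrent total bilirubin increase, in the absence of cholestasis or hemolysis". A note under the table limits it to the monitoring schedule and refers to Table 6-5 for dose changes.

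**The concern.** The same laboratory picture leads to different stopping instructions depending on which passage a site reads. Table 6-5 makes the stop unconditional for the elevated-baseline group; Section 6.2.6.1 makes it conditional.

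The group is a realistic one. Section 5.3 excludes patients only above 5 x ULN for AST/ALT and above 2 mg/dL for bilirubin, so raised baseline values are allowed. Section 6.2.6.1 itself lists liver lesions and obstruction or compression among the causes to look for.

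What is at stake is whether a patient with potential drug-induced liver injury and cholestasis is taken off treatment permanently. The rationale for Amendment 4 says that its purpose was to clarify action on study treatment in such cases, and the current text does not achieve that for this group. The SAP also tabulates permanent discontinuations with reasons (Section 2.5.2.4) and adverse events leading to discontinuation (Section 2.9.1.3). Entries for such patients would depend on the passage followed.

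**Working it through.** The plan gives no figure to reproduce. The check sets the passages side by side and then takes one patient through them.

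**Conditions on the stop**

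| Passage | Normal baseline | Elevated baseline | Role |
|---|---|---|---|
| Table 6-5 | no cholestasis required | no condition | dose modification |
| Section 6.2.6.1 | no cholestasis required | no cholestasis required | DILI follow-up, with a discontinuation instruction |
| Table 6-9 heading | no cholestasis or haemolysis | same | monitoring only |

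The first two rows agree for a normal baseline and differ for an elevated one.

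**Does other text resolve it?** Table 6-5 points to Section 6.2.6 only for further follow-up evaluations, which does not bring in a condition on stopping. Footnote b concerns patients below the thresholds. Footnote a mentions haemolysis, but only for isolated bilirubin. None of these settles the matter.

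**Worked patient (assumed values, no bone metastasis)**

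- Baseline: ALT 2.0 x ULN, bilirubin 0.9 x ULN. The raised ALT places the patient in the elevated-baseline branch. ALT is within the 5 x ULN entry limit. Bilirubin is within the 2 mg/dL limit if the local ULN is no more than 2/0.9 = 2.2 mg/dL.
- On study: ALT 5.0, bilirubin 2.5, ALP 4.0 x ULN.
- ALT: 2 x baseline = 2 x 2.0 = 4.0. 5.0 > 4.0 and 5.0 > 3.0, so the condition is met.
- Bilirubin: 2 x baseline = 2 x 0.9 = 1.8. 2.5 > 1.8 and 2.5 > 2.0, so the condition is met.
- Cholestasis: ALP 4.0 > 2.0, and R = ALT/ALP in multiples of ULN = 5.0/4.0 = 1.25 < 2, so the definition is met.

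**Result**

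- Table 6-5: permanent discontinuation.
- Section 6.2.6.1: the condition for its discontinuation instruction is not met.
- Table 6-9: the patient falls outside the heading of the combined block.
- Footnote b: does not apply, because the combined thresholds are met. No passage assigns this patient to a row on the ground of cholestasis.

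**R cut-off.** The definition uses R below 2, while the explanatory note after it (Table 6-5 and Section 6.2.6.1) calls R of 2 or less cholestatic. The two differ only at R = 2 exactly.

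**The case against.** The best reply is that the documents already rank the passages. Section 6.2.5 names Table 6-5 among the guidelines for dose modification and requires any departure to be discussed with the sponsor, whereas Section 6.2.6.1 is headed as follow-up. Section 6.2.6.1 says what to do without cholestasis and never says that a cholestatic patient may continue. It also says immediately, not permanently. On this reading a site that follows Table 6-5 breaks no rule.

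Much of that is fair, and it limits the point. But Section 6.2.6.1 contains its own discontinuation instruction on the same thresholds, with a condition that is pointless if every patient in the elevated-baseline group must stop anyway. No sentence says that Table 6-5 prevails over it, so the mismatch remains.

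Three stronger readings are tempting, and the documents do not support them:

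- *That there are three competing stopping triggers.* Table 6-9 covers monitoring and defers to Table 6-5 for dosing. Its haemolysis wording is a mismatched heading, not a third dosing rule.
- *That a site following Section 6.2.6.1 would hold and then restart the drug.* The isolated rows would give no change for ALT of 5.0 x ULN and a hold for bilirubin of 2.5 x ULN, but footnote b opens those rows only below the combined thresholds. The route is an inference; what the text leaves is a gap.
- *That site comparisons of discontinuations would be invalid.* The SAP plans none. It summarises discontinuations by treatment group.

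**Conclusion.** The text is wrong as written, within a narrow scope. For patients with raised baseline AST, ALT or bilirubin who reach the combined threshold and also meet the definition of cholestasis, Table 6-5 requires a permanent stop and Section 6.2.6.1 does not call for one. No passage says which row then applies. The Table 6-9 heading and the R wording are secondary mismatches.

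The size in patients is unknown: the documents give no frequency of cholestasis or of combined elevations. The worked patient shows that the conflict can arise within the entry limits; it is not an estimate of how often it does. The definition of the primary endpoint and the sample size are not affected. Expansion enrolment stopped after 25 December 2016 (SAP Section 1), but Amendment 6 of May 2022 still provides for patients on treatment, so the instructions remained in use.

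This conclusion rests on reading OR in Table 6-5 as separating two complete criteria, with the cholestasis condition attached to the first only, as it is printed. It takes no view on which rule is clinically right.

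**What to change.** The sponsor should reconcile Table 6-5 and Section 6.2.6.1 to a single trigger:

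1. State in each baseline branch of Table 6-5 whether cholestasis is an exception, and make Section 6.2.6.1 say the same.
2. If it is an exception, name the row that applies to a patient who meets the combined threshold with cholestasis, and adjust footnote b to match. If it is not, remove the condition from the discontinuation sentence in Section 6.2.6.1.
3. Use the same term for the stop (immediate, permanent or both) in both places.
4. Align the Table 6-9 heading with the chosen rule, including whether haemolysis matters, and use one R cut-off in the definition and in the note.

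The clinical choice belongs to the sponsor. The cost is wording in one table row and its footnotes, one paragraph of Section 6.2.6.1 and one heading, made by protocol amendment. No new tests are needed: ALT, AST, ALP and bilirubin are already measured.

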6.2.5 Dose modification and delay

For patients who do not tolerate the protocol-specified dosing scheme, dose adjustments and interruptions are permitted. All dose modifications should be based on the worst preceding toxicity (CTCAE version 4.03). Once a dose reduction has occurred, the dose level may not be re-escalated during subsequent treatment cycles with INC280. In addition, in the Dose Determining Part, a patient must discontinue treatment with INC280 if, after treatment is resumed at a lower dose, the toxicity recurs with the same or worse severity. In the Dose Expansion Part, a patient must discontinue treatment with INC280 if, after treatment is resumed at the lowest allowed dose (200 mg BID, tablet), the toxicity recurs with the same or worse severity. All interruptions or modifications to study drug administration must be recorded on the Dose Administration Record eCRF.

If a dose delay of >21 days is required, then the investigational treatment with INC280 must be discontinued. [Table 6-3](#), [Table 6-4](#), [Table 6-5](#), [Table 6-7](#) and [Table 6-8](#) provide the guidelines to be followed for dose modification of the study drug in the event of toxicities. Included are

also instructions for re-initiation of study treatment once sufficient recovery of toxicity is seen. **Any dosing modifications that are not in accordance with the guidelines in Table 6-3, Table 6-4, Table 6-5, Table 6-7 and Table 6-8 (Andrew et al 2010) must be discussed with Novartis.** Any dose change to the study drug must be recorded on the eCRF. The study visit schedule should be followed irrespective of any study drug interruption.

In exceptional situations, study treatment may continue even if there is a dose interruption of >21 days or the patient experienced disease progression. The decision to allow for continuation of treatment will be made on a case-by-case basis following discussion between Novartis and the investigator. Situations that may allow for continuation of treatment include the following:

- A dose delay of >21 days has occurred but the patient is clearly benefiting from study treatment (i.e., SD, PR, or CR) and it is the investigator's opinion that no safety concerns are present.

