Febrile neutropenia ANC < 1.0 x 10 ⁹ /L or 1000/mm ³ and a single temperature of >38.3°C (101 °F) or a sustained temperature of >=38 °C (100.4 ° F) for more than one hour.	Discontinue dose until resolved, then: If resolved in ≤ 7 days, then resume treatment at ↓ 1 dose level. If resolved in > 7 days, then discontinue dose and patient from study treatment
Platelet count decreased (Thrombocytopenia) Grade 1 or 2 (< LLN – 50x10 ⁹ /L) Grade 3 (<50 – 25x10 ⁹ /L) Grade 4 (<25x10 ⁹ /L)	Maintain dose level Discontinue dose until resolved to ≤ grade 1 or baseline, then: If resolved in ≤7 days, then maintain dose level If resolved in > 7 days, then ↓ 1 dose level Discontinue dose until resolved to ≤ grade 1 or baseline, then ↓ 1 dose level
Renal	
Serum creatinine Grade 1 (> ULN – 1.5 x ULN) Grade 2 (> 1.5 - 3.0 x ULN) Grade 3 or 4 (> 3.0 x ULN)	Maintain dose level Discontinue dose until resolved to ≤ grade 1 or baseline, then maintain dose level. Patients will be instructed to increase their fluid intake until resolution to ≤ grade 1 or baseline. Discontinue dose until resolved to ≤ grade 1 or baseline, then resume treatment at ↓ 1 dose level. Patients will be instructed to increase their fluid intake until resolution to ≤ grade 1 or baseline. If grade 4 event recurs at any point during participation, discontinue study treatment.

Recommended dose modifications of INC280	
Worst toxicity CTCAE v4.03 grade	Recommended dose modifications any time during a cycle of therapy, including intended day of dosing
Hepatic	
Isolated Total Bilirubin ^a	
Grade 1 (> ULN – 1.5 x ULN)	Maintain dose level with liver function tests (LFTs)* monitored
Grade 2 (>1.5 - 3.0 x ULN)	Omit/delay dose until resolved to ≤ grade 1 or baseline, then: If resolved in ≤ 7 days, maintain dose level If resolved in > 7 days, ↓ 1 dose level
Grade 3 (> 3.0 - 10.0 x ULN)	Omit/delay dose until resolved to ≤ grade 1 or baseline, then: If resolved in ≤ 7 days, ↓ 1 dose level If resolved in > 7 days, discontinue patient from study treatment
Grade 4 (> 10.0 x ULN)	Discontinue dose and patient from study treatment.
Isolated AST or ALT	
Grade 1 or 2 (> ULN - 5.0 x ULN)	Maintain dose level with liver function tests (LFTs)* monitored
Grade 3 (> 5.0 – 20.0 x ULN)	Omit/delay until resolved to ≤ grade 1 or ≤ grade 2 if grade 2 elevation at baseline, then: If resolved in ≤ 7 days, maintain dose level of INC280 If resolved in > 7 days, ↓ 1 dose level of INC280 Discontinue dose and patient from study treatment.

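### Table 6-5 orders both hold-and-resume and discontinuation for asymptomatic amylase or lipase above 5.0 × ULN; the concomitant-drug sections also disagree

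*Protocol*

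**What the plan says.** **Pancreatic rows (Protocol Section 6.2.5, Table 6-5).** Asymptomatic grade 1 or 2 elevations keep the dose. The next row is triggered by "Asymptomatic grade 3 or greater amylase or lipase increased (> 2.0 - > 5.0 x ULN"), and its action is "Omit/delay dose until resolved to ≤ G2, then: If resolved in ≤ 7 days, maintain dose level"; if recovery takes longer than 7 days, the dose drops one level. The row after that is triggered by "Asymptomatic grade 4 (> 5.0 x ULN"), and its action is "Discontinue does and patient form study treatment" (the two misspellings are in the document).

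**General rules in the same section.** On which grade to use: "All dose modifications should be based on the worst preceding toxicity (CTCAE version 4.03"). On sponsor involvement, discussion is required for "Any dosing modifications that are not in accordance with the guidelines in Table 6-3, Table 6-4, Table 6-5" and the related tables. Footnote b of Table 6-5 asks for the more conservative action, but it opens with "If combined elevations of AST or ALT and total bilirubin do not meet the defined thresholds" and so concerns liver tests only.

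**Concomitant drugs.** Section 6.3.3 prohibits strong CYP3A4/5 inhibitors, strong CYP3A4/5 inducers, and narrow-window substrates of CYP1A2 or CYP3A4/5, and points to Appendix 4 for the list. Exclusion criteria 20 and 21 take the same line. Table 14-9 in Appendix 4, the prohibited list, has a single row: strong CYP3A4 inducers. Section 6.3.2 and Table 14-10 allow strong CYP3A inhibitors with monitoring. For narrow-index CYP1A2 substrates, Section 6.3.2 says to avoid them but allows a reduced substrate dose when they cannot be avoided, and Table 14-10 lists them as permitted with caution. Table 14-10 also names grapefruit juice, which Section 6.1.1.1 tells patients to avoid.

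**The concern.** A dose-modification table should give one action for one finding. Here, two sites seeing the same asymptomatic grade 4 lipase could act in opposite ways, one restarting the drug at full dose after a week and the other stopping it for good. Each could point to a row that supports it.

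The rule can still be triggered. Amylase and lipase remain mandatory at every visit under the reduced schedule in Table 7-2, and Section 1.2.1.1.3 names the pancreas as a target organ in the toxicology studies.

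For the drug lists, a site whose patient needs a strong CYP3A inhibitor or a narrow-index CYP1A2 substrate cannot tell whether giving it is a deviation. Section 12 bars sites from asking the sponsor to approve deviations, so the text itself has to be clear.

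**Working it through.** No sample size, power or event figure is involved. The check compares trigger ranges and drug classes.

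**Step 1. Ranges of the asymptomatic pancreatic rows.** Let x be the value as a multiple of ULN.

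- Maintain row (grade 1 or 2): 1 < x ≤ 2.
- Hold row (grade 3 or higher; its written upper end is itself a greater-than sign at 5.0): x > 2, with no cap.
- Grade 4 row: x > 5.

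The hold and grade 4 rows overlap wherever x > 5. The grade 4 row therefore lies wholly inside the hold row.

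| x | Rows met |
|---|---|
| 1.5 | maintain |
| 3 | hold |
| 5.0 | hold |
| 5.1 | hold and discontinue |
| 6 | hold and discontinue |
| 10 | hold and discontinue |

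A PDF-reading fault is unlikely to explain this, because the row's words and its numeric range each include grade 4 independently.

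**Step 2. Does any stated rule settle it?**

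- The worst-toxicity rule fixes the grade at 4, but grade 4 satisfies both rows.
- Footnote b applies to AST or ALT combined with bilirubin, not to pancreatic enzymes.
- The sponsor-discussion clause covers changes that depart from the guidelines. Resuming follows one row and departs from the other, so the clause does not decide.

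**Step 3. What the rest of Table 6-5 does at grade 4.** Eight other blocks state a grade 4 action.

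- Discontinuation without exception, 5: ANC, isolated AST/ALT, cardiac, ILD/pneumonitis, other adverse events.
- Discontinuation with an exception, 1: isolated bilirubin. Footnote a allows one level down for an indirect-only rise above 3.0 × ULN once hemolysis is excluded, with no upper cap.
- Hold, then one level down, 2: platelets ("Discontinue dose until resolved to ≤ grade 1 or baseline, then ↓ 1 dose level") and creatinine (where a recurrent grade 4 event means stopping).

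Total: 5 + 1 + 2 = 8.

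**Step 4. Where grade 3 ends in blocks with separate numeric grade 3 and grade 4 rows.**

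| Block | Grade 3 ends at | Grade 4 starts at |
|---|---|---|
| ANC (/mm³) | 500 | 500 |
| Platelets (×10⁹/L) | 25 | 25 |
| Bilirubin (× ULN) | 10 | 10 |
| AST/ALT (× ULN) | 20 | 20 |
| Amylase/lipase (× ULN) | not closed | 5 |

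Four of five are closed; only the pancreatic block is open.

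**Step 5. CYP classes prohibited in Section 6.3.3, set against Appendix 4.**

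| Class | Table 14-9 (prohibited) | Table 14-10 (caution) |
|---|---|---|
| Strong CYP3A inducers | yes | no |
| Strong CYP3A inhibitors | no | yes, 27 entries |
| Narrow-index CYP1A2 substrates | no | yes, 2 entries |
| Narrow-window CYP3A4/5 substrates | no row | no row |

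Appendix 4 has a tie-break, the stricter rule, but only for a drug that appears in both tables. None of the 27 + 2 = 29 entries is among the 9 in Table 14-9, so the tie-break settles none of them.

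**The case against.** **The grade 4 row is the specific one.** Table 6-5 is entered by worst grade, and a grade 4 patient has a row carrying that label. Restarting contradicts that row, so it is arguably off-guideline and needs sponsor discussion. Stopping is always open to the investigator under Section 7.1.4.1. This makes discontinuation the likely intent and means a cautious site is not in breach. It does not supply a precedence rule, and the other site can still cite the hold row.

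**The protocol groups grade 3 and above elsewhere.** Table 6-2 counts asymptomatic grade 3 or higher as a qualifying event only if it lasts more than 14 consecutive days. Table 6-6 and footnote d also treat grade 3 and above together. These passages govern event counting, follow-up and imaging, not dosing. They are still a fair reason to have the sponsor confirm the intent.

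**A stronger reading is tempting but fails.** A reader might infer that the hold row is the only place where a grade 4 toxicity may restart at the same dose. It is not. Hepatitis B reactivation is recorded as grade 4 when life-threatening, and Table 6-7 lets a patient already on the lowest dose restart at that dose after resolution within 21 days. Nor do six of the eight other blocks stop without exception, because bilirubin carries the footnote a exception.

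**The drug-list conflict is modest.** By Section 6.3.2, a strong inhibitor raises INC280 AUCinf by 42% with Cmax unchanged. Section 1.2.1.2.3 reports AUC variability of 42% and 65%, and no MTD has been defined. Withholding the drug satisfies both texts, so the conflict bites only when a patient needs one. The two grapefruit juice instructions differ in degree and are not opposites. All of this stands and makes the drug-list issue secondary.

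**Conclusion.** The overlap is real in the current operative text: two incompatible actions apply to every asymptomatic amylase or lipase value above 5.0 × ULN. Discontinuation is the better-supported reading, because a separate grade 4 row would be pointless if the hold row covered grade 4, and the four comparable blocks close grade 3. That is an inference about intent, not a stated rule.

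The drug-class mismatch is also confirmed: of four classes prohibited in Section 6.3.3, one agrees with Appendix 4, two conflict and one is unlisted.

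The reach is limited. The SAP introduction says no patients are enrolled after 25-Dec-2016, so only patients still on treatment can be affected, and the visible text does not say how many remain. A reader might infer that the trial's results are in doubt; the documents do not support that. The TTP analysis, sample size, operating characteristics and analysis sets do not depend on either point.

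**What to change.** 1. **Table 6-5.** Reword the hold row to asymptomatic grade 3 only, above 2.0 and up to 5.0 × ULN, so that grade 4 means discontinuation only. The sponsor should confirm that this is the intent.
2. **Drug classes.** The sponsor sets one status each for strong CYP3A inhibitors, narrow-index CYP1A2 substrates and narrow-window CYP3A4/5 substrates, then aligns Sections 6.3.2 and 6.3.3 and Tables 14-9 and 14-10.
   - If prohibited: keep the class in 6.3.3, give it a row in Table 14-9, and remove it from 6.3.2 and Table 14-10 where it appears there.
   - If caution: take the class out of 6.3.3, and keep or add it in 6.3.2 and Table 14-10. For strong inhibitors, also amend exclusion 20, whose wording extends through the study and would otherwise still conflict.
3. **Grapefruit juice.** Remove it from Table 14-10 to match Section 6.1.1.1.

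The cost is one table row and some concomitant-drug wording in the next amendment. An interim letter to sites is optional and should carry the same content. Sample size and planned analyses stay as they are.
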